1.2 Schedule of Activities (SoA)

Table 1Schedule of Activities

	Screening		3-Way Crossover Period					End of Study Evaluation	
Procedures	V1	V2	V3	Wash-out	V4	Wash-out	V5	Wash-out	Evaluation
Trial Day (Visit Window)	Up to 4 weeks		Up to 6 weeks					2 wks post $V5 \pm 3 d$	
Informed consent	X								
Non-PSG enrollment criteria ²	X								
Demography	X								
Physical exam	X								
Medical history	X								
Clinical laboratory testing	X								X
Pregnancy test ³	X								
12 Lead ECG	X								
PSG Exam		X ⁴	X		X		X		
Randomization ⁵			X						
HS study treatment ⁶			X		X		X		
DSST, KSS, Sleep quality VAS ⁷			X		X		X		
Vital signs ⁸	X	X	X		X		X		
AE/SAE monitoring			X	X	X	X	X	X	X
Prior/concomitant medication	X	X	X	X	X	X	X	X	X

6 January 2021 7 of 54 V2.0

¹ Each washout period is a minimum of 7 days

² Includes ESS, PGI-S, and history of OSA symptoms

³ WOCBP only

⁴ Only patients who meet all non-PSG enrollment criteria at Visit 1 are eligible for a screening PSG

⁵ Randomization occurs when participant meets enrollment criteria up to the time of the first crossover period.

⁶ Study medication administered immediately before lights out

⁷ Administer at similar time after awakening after each crossover PSG, approximately 1 hour after awakening

⁸ Vital signs include the following: seated blood pressure, pulse, respiratory rate; vital signs on PSG nights taken after admission to PSG lab.

Clinical Study Protocol CONFIDENTIAL

Abbreviations: AE = adverse event; DSST = Digit Symbol Substitution Test; ECG = electrocardiogram; ESS = Epworth sleepiness scale; KSS = Karolinska sleepiness scale; PGI-S = patient global impression of severity of OSA; PSG = polysomnography; SAE = serious adverse event; VAS = visual analog scale; WOCBP = women of childbearing potential.

6 January 2021 8 of 54 V2.0

2 Introduction

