7.1.1 Polysomnography

- Methods: Standard overnight PSG recording and data interpretation will be performed in accordance with the American Academy of Sleep Medicine (AASM) scoring manual.
 Participants will be instrumented with standard PSG electrodes. Time of lights out will be established according to the participants' habitual schedule and kept constant across the PSG study nights. The participants will be given 8 hours of time-in bed.
- Scoring: All PSG studies (including screening PSG) will be scored by centralized PSG technologists, blinded to treatment assignment. Scoring will be conducted according to the American Academy of Sleep Medicine manual scoring criteria.

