3.2.3. Dosing Schedule

There are 3 randomized crossover PSG nights. The participant will receive one treatment on each of the 3 PSG nights, separated by at least a one-week washout period. Dosing of the study treatment will occur immediately prior to lights out.

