4.4. Handling of Dropouts or Missing Data

Missing data will remain missing. No imputation of missing data will be performed.

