7.2.1. Treatment-emergent Adverse Events

A treatment-emergent adverse event (TEAE) is defined as any event not present prior to exposure

of study drug or an event already present that worsens in either severity or frequency following exposure. Each TEAE is assigned to the most recent study treatment administered on or before the TEAE's date of onset.

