All occurrences of all AEs will be listed for each participant, grouped by treatment. The listing will contain the following information: treatment sequence, study treatment, SOC, PT, verbatim term, intensity, relationship to study medication, date and study day of onset, date and study day of resolution, treatment given to treat the adverse event, action taken, the outcome, whether the event was an SAE, whether it led to withdrawal. Listings will be sorted by treatment sequence, participant identification number, onset date, SOC, and PT. If onset year is non-missing but month and/or date is missing, then the day of the most recent study drug dose will be imputed as onset date.

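### Adverse events that begin on the V4 or V5 date before the bedtime dose are booked to a treatment not yet taken

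*SAP*

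**What the plan says.** SAP 7.2.1 first defines a treatment-emergent event (TEAE): one absent before exposure, or "an event already present that worsens in either severity or frequency following exposure". It then gives the allocation rule: "Each TEAE is assigned to the most recent study treatment administered on or before the" event's onset date. The rule has no time element.

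SAP 3.2.3 fixes when the tablet is taken: "Dosing of the study treatment will occur immediately prior to lights out". A footnote to the Protocol 1.2 schedule agrees: "Study medication administered immediately before lights out". No clock time is given; Protocol 7.1.1 says only "Time of lights out will be established according to the participants' habitual schedule".

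The adverse event listing in SAP 7.2.5 shows the date and study day of onset, with no time and no before/after-dose indicator. The same paragraph covers incomplete dates: "If onset year is non-missing but month and/or date is missing, then the day of the most recent study drug dose will be imputed" as the onset date. SAP 4.4, however, states "No imputation of missing data will be performed" and names no exception.

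**The concern.** With a bedtime dose, the dosing date and the exposed period hardly overlap: the date is almost over when the tablet is swallowed. A rule that counts a dose given on the onset date as already taken therefore gives the wrong answer for any event that starts during that day. Such events can be captured. Adverse events are collected from randomization (Protocol 7.3.1) and recorded at each visit, and vital signs on PSG nights are taken after admission to the laboratory.

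TEAE incidence, intensity, relatedness and discontinuation are all tabulated by treatment (SAP 7.2.5). Comparing the safety of two doses and placebo is part of the primary objective (SAP 2.1.1). With 30 participants, one or two misplaced events can visibly change a column.

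The partial-date rule raises a smaller, related question. It does not say what *most recent* is measured from, and it does not use a month that is known.

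**Working it through.** The plan states no figure that depends on this rule, so there is none to reproduce. The check applies the rule hour by hour and compares it with the last dose actually taken.

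**Inputs from the documents**
- Allocation is to the latest dose whose date is on or before the onset date (SAP 7.2.1).
- Dosing is at lights out (SAP 3.2.3; Protocol 1.2).
- There are three doses, at V3, V4 and V5, with each washout at least 7 days (Protocol 1.2).
- The end-of-study evaluation is 2 weeks after V5 (Protocol 1.2).
- Five blocks each contain all six sequences once (SAP 3.2.1).

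**Assumptions**
- Lights out at 21:00, 22:00 or 23:00.
- 7 or 14 days between doses.
- Exactly 14 days of follow-up after V5.
- Events uniform in time.

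**Worked example.** Sequence ABC, lights out 22:00, V3 on 22 February, V4 on 1 March, V5 on 8 March.

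| Onset | SAP rule gives | Last dose actually taken |
|---|---|---|
| 1 March 10:00 | B | A |
| 1 March 23:00 | B | B |
| 2 March 07:00 | B | B |
| 8 March 18:00 | C | B |

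Only onsets on the V4 or V5 date before the dose are wrong. Onsets during the dosing night and on the next day are right.

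**Size.** The misassigned window before a dose runs from midnight to the dose, so its length in hours equals the clock hour of dosing, *h*. Two doses (V4, V5) are affected, giving 2*h* hours per participant. A 7-day interval has 168 hours and a 14-day interval 336. From first dose to end of study there are (7+7+14)×24 = 672 hours, or (14+14+14)×24 = 1008 hours.

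| Lights out | 2*h* | Share of 7-day interval, *h*/168 | Share of 14-day interval, *h*/336 | Share of all time, 7-day spacing, 2*h*/672 | Share of all time, 14-day spacing, 2*h*/1008 |
|---|---|---|---|---|---|
| 21:00 | 42 | 12.5% | 6.3% | 6.3% | 4.2% |
| 22:00 | 44 | 13.1% | 6.5% | 6.5% | 4.4% |
| 23:00 | 46 | 13.7% | 6.8% | 6.8% | 4.6% |

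A participant whose habitual lights out falls after midnight would have almost no affected time, since *h* is then close to zero.

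**Direction.** The six sequences contain 12 treatment-to-treatment transitions. Each of the six ordered pairs occurs twice; A followed by B, for example, occurs in ABC and CAB. Five blocks give 10 of each ordered pair if everyone completes. Each treatment therefore loses 20 affected windows to its successors and gains 20 from its predecessors. If the background event rate is the same throughout, expected gains and losses are equal for every pair of treatments.

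**Does a one-word change work?** Dropping the same-day dose (strictly before, instead of on or before) would send the 1 March 23:00 event to A, although B was taken at 22:00. Date alone cannot separate the two cases.

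**Partial dates.** Suppose only the month, February, is known in the example above. If *most recent* is measured from the report date or from the last dose overall, the imputed date can be 1 or 8 March, which contradicts the known month. If it is measured from the possible onset, the imputed date is 22 February. The SAP does not say which reading applies.

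**The case against.** The best case for leaving the rule alone is that little depends on it. The affected window is the last 21 to 23 hours of a washout of at least 7 days after a single dose. The safety analysis is descriptive (SAP 7), so no test uses the allocation. Investigators weigh the timing of each event against dosing when they judge causality (SAP 7.2.3), TEAEs are also tabulated by relationship, and every event is listed with its treatment and onset date. The eCRF is not among the documents and may already collect an onset time. All of this stands as a limit on the harm. None of it corrects the table entry, because the SAP rule would not use a time even if one were recorded.

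A reader might infer more than the documents support:

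- *That pre-dose events on the V3 date become treatment-emergent.* The definition in SAP 7.2.1 already excludes an event present before exposure, and the date rule applies only to TEAEs. What is missing at V3 is a time or flag with which to apply that definition.
- *That events on the drug night or after midnight go astray.* They are assigned correctly. So is an event reported at V4 or V5 admission that began on an earlier day.
- *That about 13% of all events are misassigned.* That figure is for a 7-day interval ending in another dose, with a flat event rate. The last treatment is followed by two weeks with no further dose, so the share of all time is about 4–7%, and it is lower still if events cluster after dosing.
- *That drug effects are systematically moved to placebo and real differences diluted.* This needs treatment-specific events that begin roughly six to seven days after one dose, which nothing in the documents suggests. For background events the balanced sequences equalise the transfers in expectation.
- *That the partial-date rule also books events to a treatment not yet taken.* *Most recent* ordinarily means a dose already given. The rule sits in the listing paragraph, so its use for allocation is an inference. With contact at every visit and by telephone in each washout, incomplete dates should be few. The conflict with SAP 4.4 is a specific rule against a general one.

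**Conclusion.** The point holds for a definite class of events: onsets on the V4 or V5 calendar date before that night's dose. For these, the rule in SAP 7.2.1 names a treatment not yet taken, and nothing elsewhere in the SAP repairs it. Per participant this is 42–46 hours, under the lights-out, spacing, follow-up and flat-rate assumptions set out above.

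The consequence is modest noise in the by-treatment adverse event tables, not an identifiable bias for or against any treatment. The balance argument is exact only if all 30 participants complete; withdrawals are not replaced, so it is otherwise approximate. An error from the partial-date rule is possible but not certain. Efficacy results are untouched. The repair is cheap enough to be worth making before the tables are produced.

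**What to change.** **SAP 7.2.1.** For an onset on a dosing date, assign by onset time relative to dose time, or by a before/after-dose flag if time is not collected. Pre-dose onsets on the V4 or V5 date go to the previous treatment. On the V3 date, use the same time or flag to apply the existing TEAE definition. This brings the misassigned hours from 42–46 per participant to zero.

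**SAP 7.2.5.** For a partial onset date, use the most recent dose on or before the latest date consistent with the known parts of the onset date and with the resolution or report date. Never override a known month: if no dose falls in that month, use the dose for treatment assignment only and leave the month as recorded. A rule that takes the first dose within the known month would not do, because there may be no dose in it.

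**SAP 4.4.** Name this as the exception to the no-imputation statement.

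**Cost.** One eCRF field at most, and none if onset times are already recorded, plus SAP wording. Design, dosing and efficacy analysis do not change.

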1.1 Synopsis

Protocol Title:

Sponsor Study No.:

Phase: 2

Sponsor: Apnimed, Inc.

Rationale:

Apnimed is developing the combination of atomoxetine and oxybutynin for the treatment of obstructive sleep apnea (OSA). Initial Phase 2 studies of the combination were conducted with marketed oxybutynin (combination designated AD-036), which is a racemic mixture of R- and S-oxybutynin. Subsequent development is being pursued with R-oxybutynin (combination designated AD-109), a new enantiomerically pure form of oxybutynin which is proposed to have an improved safety and efficacy profile in OSA compared to racemic oxybutynin.

Previous studies of AD-036 provided dose-response efficacy and safety data across a broad spectrum of OSA disease severity. Study APC-004 is designed to extend and confirm these findings to AD-109 in a population with mild- to moderate OSA, in parallel with other studies of AD-109 planned by Apnimed in moderate- to severe OSA.

Overall Design:

Study APC-004 is a randomized, double blind, placebo-controlled, 3-period, single-dose crossover study in patients with mild- to moderate OSA. A screening visit and polysomnographic (PSG) exam will be conducted to establish that each participant meets study enrollment criteria. Each participant will then receive a single dose of each of the following during 3 overnight PSG exams, each separated by a one week washout period:

- Atomoxetine 75 mg + R-oxybutynin 2.5 mg (i.e. 75/2.5)
- Atomoxetine 37.5 mg + R-oxybutynin 2.5 mg (i.e. 37.5/2.5)
- Placebo

Primary efficacy and safety endpoints will compare the 75/2.5 and 37.5/2.5 doses to each other and to placebo.

Number of Participants:

A total of 30 participants will be enrolled.

Study Duration:

The overall study duration will be up to 12 weeks, as follows:

- Screening, up to 4 weeks;
- 3-period crossover, up to 6 weeks;
- End of Study Evaluation, 2 weeks post crossover period

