6.6 Stopping Criteria

6.6.1 Individual Participant Stopping Criteria

- Incidents of abuse, diversion, or misuse of the study treatment.
- Incidents of clinical significance: hallucinations, amnesia, delusional thinking, delirium, manic symptoms, aggressive behavior, suicidality, homicidality, agitation, confusion, or convulsions/seizures.
- Participants reporting any SAE considered possibly related or related to study treatment.
- Acute urinary obstruction.
- Any other AE that in the judgment of the Investigator necessitates the participant stopping to protect participant safety.

Participants discontinued from dosing will undergo end of study procedures with follow-up monitoring of the AE(s) as clinically indicated.

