9.2 Appendix 2: Clinical Laboratory Tests

- The tests detailed in Table 2 will be performed by the local laboratory.
- Laboratory testing is performed non-fasting.
- Additional tests may be performed at any time during the study as determined necessary by the Investigator or required by local regulations.

Table 2: Protocol-Required Safety Laboratory Assessments

Laboratory Assessments	Parameters		
Hematology	Hematocrit Hemoglobin Platelet Count RBC Count	RBC Indices (MCV, WBC count with Differential MCH, MCHC)	
Serum Chemistry	Albumin BUN Creatinine Potassium Sodium Bilirubin (total) Total Protein Uric acid	ALT AST Alkaline phosphatase Calcium Glucose Total cholesterol Chloride Bicarbonate	
Routine Urinalysis	 Specific gravity, bilirubin, color, appearance, leukocyte esterase, nitrite, pH, protein (albumin), glucose, ketones, occult blood, urobilinogen Reflex microscopy 		
Other Tests	 HbA1c (Screening Visit only) Serum hCG pregnancy test at screening. Additional testing may be performed if needed in WOCBP. Urine test of drugs of abuse (marijuana, cocaine, amphetamine, methamphetamine, opiates, phencyclidine) 		

Abbreviations: ALT = alanine aminotransferase; AST = aspartate aminotransferase; BUN = blood urea nitrogen; HbA1c = hemoglobin A1c (glycated hemoglobin); hCG = human chorionic gonadotropin; RBC = red blood cell count; WBC= white blood cell; WOCBP = women of childbearing potential.

Investigators must document their review of each laboratory safety report.

9.3 Appendix 3: Adverse Events: Definitions and Procedures for Recording, Evaluating, Follow-up, and Reporting

Definition of AE

AE Definition

- An AE is any untoward medical occurrence in a participant or clinical study participant, temporally associated with the use of a study treatment, whether or not considered related to the medicinal product.
- NOTE: An AE can therefore be any unfavorable and unintended sign (including an abnormal laboratory finding), symptom, or disease (new or exacerbated) temporally associated with the use of a study treatment.

Events Meeting the AE Definition

- Any abnormal laboratory test results (hematology, clinical chemistry, or urinalysis) or
 other safety assessments (e.g., ECG, radiological scans, vital signs measurements),
 including those that worsen from baseline, considered clinically significant in the
 medical and scientific judgment of the Investigator (i.e., not related to progression of
 underlying disease).

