7.4. Clinical laboratory values

Clinical laboratory values will be summarized by presenting descriptive statistics of actual values and changes from baseline for the end of study evaluation. Clinical laboratory values include urinalysis (dipstick and microscopic), hematology, and chemistry lab values. A by-participant listing of clinical laboratory values will also be provided.

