10. APPENDICES

10.1. Appendix A: Schedule of Activities

Procedures	Screening		3-Way Crossover Period						End of Study Evaluation
	V1	V2	V3	Wash-out ¹	V4	Wash-out	V5	Wash-out	
Trial Day (Visit Window)	Up to 4 weeks		Up to 6 weeks						2 wks post V5 ± 3 d
Informed consent	X								
Non-PSG enrollment criteria ²	X								
Demography	X								
Physical exam	X								
Medical history	X								
Clinical laboratory testing	X								X
Pregnancy test ³	X								
12 Lead ECG	X								
PSG Exam		X ⁴	X		X		X		
Randomization ⁵			X						
HS study treatment ⁶			X		X		X		
DSST, KSS, Sleep quality VAS ⁷			X		X		X		
Vital signs ⁸	X	X	X		X		X		
AE/SAE monitoring			X	X	X	X	X	X	X
Prior/concomitant medication	X	X	X	X	X	X	X	X	X

¹ Each washout period is a minimum of 7 days

² Includes ESS, PGI-S, and history of OSA symptoms

³ WOCBP only

⁴ Only patients who meet all non-PSG enrollment criteria at Visit 1 are eligible for a screening PSG

⁵ Randomization occurs when participant meets enrollment criteria up to the time of the first crossover period.

⁶ Study medication administered immediately before lights out

⁷ Administer at similar time after awakening after each crossover PSG, approximately 1 hour after awakening

⁸ Vital signs include the following: seated blood pressure, pulse, respiratory rate; vital signs on PSG nights taken after admission to PSG lab.

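### A laboratory adverse event first found at the End of Study sample is booked to the last treatment taken, although no scheduled sample can show which of the three treatments came before it

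*SAP*

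**What the plan says.** SAP 7.2.1 has one attribution rule for treatment-emergent adverse events (TEAEs): "Each TEAE is assigned to the most recent study treatment administered on or before the TEAE's date of onset". There is no upper limit on the interval and no separate category for findings made at the end of the study. SAP 7.2.5 tabulates TEAEs by study treatment, as numbers and percentages of participants. Its rule for partial onset dates also falls back on the most recent dose.

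The row "Clinical laboratory testing" in the schedule of activities (Protocol 1.2 and SAP Appendix A) is marked twice, at V1 and at the End of Study Evaluation. A footnote to the schedule says "Each washout period is a minimum of 7 days". The final evaluation is 2 weeks ± 3 days after V5.

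Protocol Appendix 3 counts abnormal laboratory results as adverse events when the investigator judges them clinically significant. SAP 7.4 summarises laboratory values as actual values and "changes from baseline for the end of study evaluation", with no split by treatment. Unscheduled sampling is allowed: "Additional tests may be performed at any time during the study as determined necessary by the Investigator" (Protocol 9.2).

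SAP 3.2.1 randomises in 5 blocks of 6, one participant per block to each of the six treatment orders. SAP 2.1.1 makes the safety comparison of the two doses with each other and with placebo part of the primary objective.

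**The concern.** A completer's End of Study sample is drawn after all three treatments, and the schedule provides no laboratory result between the V3 dose and that sample. If it shows a new abnormality, the data do not say whether it arose in period 1, 2 or 3. The rule in SAP 7.2.1 nevertheless puts the event in the column of the treatment given at V5. Among participants whose last treatment was placebo, an abnormality caused by either active dose would be shown as a placebo event.

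Safety is analysed descriptively (SAP 7), so the by-treatment counts are the result, and no model corrects them afterwards. The investigator's causality judgement is recorded but does not change the column. With 30 participants, one misplaced laboratory event is visible in the table.

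**Working it through.** **Inputs**
- Sequences ABC, ACB, BAC, BCA, CAB, CBA, where A = 75/2.5, B = 37.5/2.5 and C = placebo; 5 participants each (SAP 3.2.1).
- Washouts of at least 7 days; End of Study 14 ± 3 days after V5, so 11 to 17 days (schedule of activities).
- Assumption: the onset of an abnormality first seen in the End of Study sample is recorded after V5. The documents do not say how such an onset is dated.

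**Step 1. Reproduce the plan's number.** 5 blocks × 6 sequences = 30 participants, as stated.

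**Step 2. Which treatment is last.** Each treatment is last in 2 of 6 sequences, so in 2 × 5 = 10 of 30 participants if all complete. Placebo is last in ABC and BAC. All 10 of those participants have already taken both active doses.

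**Step 3. Where an abnormality caused by A is booked.**
- A in period 3 (BCA, CBA): booked to A, which is correct.
- A in period 2 (BAC, CAB): booked to C and to B.
- A in period 1 (ABC, ACB): booked to C and to B.

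Let d1, d2 and d3 be the chances that an abnormality caused in period 1, 2 or 3 is still present at End of Study. The share booked correctly is d3 / (d1 + d2 + d3). The rest is split equally between the other two treatments. By symmetry the same holds for B.

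**Step 4. Range of the result.**
- Equal detectability (d1 = d2 = d3): 1/3 correct, 1/3 to the other active dose and 1/3 to placebo, so 2/3 are wrong. The expected count of these events is then the same in each column whichever treatment caused them.
- Resolution over time: an effect of the V4 dose must last at least 7 + 11 = 18 days to be seen, and one of the V3 dose at least 7 + 7 + 11 = 25 days. After the V5 dose, 11 to 17 days suffices. As an illustration, assume that detectability halves every 7 days, with intervals of 7, 7 and 14 days. The relative weights for periods 3, 2 and 1 are 1, 0.5 and 0.25. Correct: 1 / 1.75 = 57%. Wrong: 0.75 / 1.75 = 43%, of which half, about 21%, goes to placebo.
- Complete resolution before day 18: d1 = d2 = 0, and every such event is booked correctly.

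If detectability does not rise with time since the dose, the wrongly booked share lies between 0 and 2/3.

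**Step 5. Is any treatment favoured?** The guaranteed adverse event follow-up is 7 days after V3, 7 after V4 and 11 after V5. Each treatment occupies each period equally often, so its mean is (7 + 7 + 11) / 3 = 8.33 days for all three treatments. With 14 days after V5 the mean is 9.33, and with 17 days it is 10.33, again equal. Each treatment also receives 10 of the 30 End of Study panels. Among completers there is no directional bias.

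**The case against.** The strongest reply is that little depends on this. Most-recent-treatment assignment is clear and reproducible. SAP 7.4 does not split laboratory values by treatment, so only findings recorded as adverse events are affected. Unscheduled tests may catch some abnormalities earlier, and Protocol 7.2.4 requires clinically relevant local results to enter the eCRF. The adverse event listing gives sequence, treatment, onset date and study day, and causality must weigh the timing relative to dosing. All of this stands, and it keeps the severity low. It does not make the column in the by-treatment table correct, and a reader of that table would not see that the attribution has no basis.

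Three stronger readings are tempting.

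- A reader might infer that periods 1 and 2 have no post-dose laboratory coverage at all. The documents support only that none is scheduled.
- A reader might infer that unequal follow-up by period biases the dose-versus-placebo comparison. Step 5 shows equality by treatment for completers. After early stopping, Protocol 6.6.1 says "Participants discontinued from dosing will undergo end of study procedures", so the sample follows the last dose actually taken. Balance could then be lost, but the documents give no figure from which to size this.
- A reader might infer that the open-ended window needs a cap. Assume a 5% weekly background and a 20% drug effect, neither from the documents. The ratio of incidences is 4.8 with a 7-day window, 3.8 at 7/7/14 days and 2.9 at 14/14/14. It is lowest of these where the windows are long but equal, so the driver is window length and not inequality. Even at 21/21/14 days the risk difference falls only from 0.19 to 0.17, and the SAP plans percentages, not ratios.

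**Conclusion.** The point holds for one class of event: a clinically significant laboratory abnormality whose only evidence is the End of Study sample, in a participant who received more than one treatment. SAP 7.2.1 gives such an event a treatment label that the data cannot support. If all complete, that label is placebo for 10 of 30 participants. The share booked wrongly is at most 2/3, reached only if the abnormality is equally detectable whichever period caused it. It falls as resolution over time becomes more important, to 43% in the illustration.

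The effect is to pull the treatment columns together for these events, without favouring any treatment among completers. Few such events are expected and safety is descriptive, so severity is low. The result rests on the End of Study finding being dated after V5 and on no informative unscheduled test having been done earlier. The documents do not support a wider claim that adverse event ascertainment is biased between treatments.

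**What to change.** Amend SAP 7.2.1 and 7.2.5 as follows. In a participant who received more than one study treatment, a TEAE whose only evidence is the End of Study laboratory sample is not assigned to a single treatment. It appears in a separate column, 'after all treatments received', with the treatment sequence, and stays in the overall totals and listings. The column refers to the treatments that the participant actually took, so it also covers someone who stopped after two doses. A participant who took only one treatment stays under the present rule, as does an event with earlier evidence such as symptoms or an unscheduled test. This agrees with SAP 7.4, which already presents End of Study laboratory values without a split by treatment.

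The cost is SAP wording and one extra column, with no new visits, samples or participants. The small downside is that these events leave the by-treatment columns. The change does not recover laboratory information for periods 1 and 2.

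A supplementary table limited to a fixed post-dose window, for example the 7-day minimum washout, could be offered. It is optional: the documents give no onset data to support a cut-off, and reasonable statisticians differ on it.
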